## 1 Protocol Flowchart

**Figure 1: Protocol flowchart**

The My-AHA RCT protocol comprises 6 elements that will be described in detail below:

1. Participant recruitment
2. Participant screening
3. Randomised allocation to control or intervention arm
4. Periodic assessments
5. Interventions
6. My-AHA User Platform interface

## 2 Recruitment

### 2.1 Type and Number of Participants

Participants will be adults aged 60 years and older meeting study inclusion criteria for pre-frailty (Table 2) and not meeting study exclusion criteria for clinically significant cognitive and/or mood disturbance (Table 4) or for concomitant diseases (see Section 3.2).

A total of 50 participants will be recruited from the Sunshine Coast region. Participants will be community residing older adults, residing either in their own home/unit, retirement community, or residential aged care (non-secure). The majority are likely to be living in a semi-supported independent living setting receiving some aged care support services in own home/residence but otherwise fully independent.

Participants who volunteer to participate in the RCT must be screened to ensure that each participant meet all inclusion criteria (Table 1) and do not meet any exclusion criteria (Table 3).

---

### 3 Participant Screening

#### 3.1 Inclusion Criteria

**Table 1:** *My-AHA RCT inclusion criteria for participant screening*

#### **INCLUSION CRITERIA**

---

1. Age: over 60 yrs
2. Familiar with use of smartphones and/or tablet computers
3. Have access to WiFi connection and existing internet data plan and provider
4. Able to stand and walk unassisted
5. Free of significant cognitive impairment (age-corrected MMSE  $\geq 24$ ) (Table 4)
6. Free of clinically significant mood disturbance (HADS-Anxiety  $<15$ ; HADS-depression  $< 15$ ) (Table 4)
7. Free of any acute or unstable medical conditions
8. Meet criteria for pre-frail status (Table 2)
9. Able to understand directions and participate in the protocol
10. Able to sign informed consent

---

**Table 2: Pre-frail inclusion criteria for participant screening**

Clinical sign/symptom	Measure	Cutoff values			
PHYSICAL DOMAIN					
Pre-frail = 1 or 2 of the following criteria are met					
1. Shrinking, evidenced by weight loss (unintentional)	$\geq 4.5$ kg unintentional in prior 12 months; or at follow-up assessment $\geq 5\%$ of body weight in prior 12 months	Self-reported weight loss (not due to dieting or fasting) in preceding 12 mo $\geq 4.5$ kg Follow-up: $K = (\text{weight in previous year} - \text{current measured weight}) / (\text{weight in previous year})$ . If $K \geq 0.05$ , meets weight loss frailty criteria			
2. Weakness	Grip strength in lowest 20% at baseline adjusted for gender and BMI	BMI Men BMI $\leq 24$ Men BMI 24.1 - 26 Men BMI 26.1 - 28 Men BMI $> 28$  Women BMI $\leq 23$ Women BMI 23.1 - 26 Women BMI 26.1 - 29 Women BMI $> 29$	Grip strength cutoff (kg) $\leq 29$ $\leq 30$ $\leq 30$ $\leq 32$  $\leq 17$ $\leq 17.3$ $\leq 18$ $\leq 21$		
3. Poor endurance and energy	Self-report of exhaustion as indicated by responses to 2 questions on CES-D scale	Using the CES-D Depression Scale, response of “2” (a moderate amount of the time, 3-4 days) or “3” (most of the time) to either of the following 2 items: (a) I felt that everything I did was an effort; and/or (b) I could not get going.			
4. Slowness	Time to walk 15ft (4.57m) $\leq$ slowest 20% adjusted for gender and standing height	Gender/Height (cm) Men Height $\leq 173$ cm Men Height $> 173$ cm Women Height $\leq 159$ cm Women Height $> 159$ cm	Cutoff time to walk 4.00 m) $\geq 6.13$ sec $\geq 5.25$ sec $\geq 6.13$ sec $\geq 5.25$ sec		

5. Low physical activity level	Energy expenditure per week below established cutoff	Short version of the IPAQ questionnaire assesses activity levels for walking, moderate-intensity and vigorous-intensity activities for work, transportation, domestic chores, gardening and leisure-related activities.	IPAQ Activity level measures as MET-min units). Convert IPAQ Met-min units to kcal using following formula adjusting for participants weight in kg: $[\text{kcal} = \text{MET-min} \times (\text{weight kg}/60)]$ Gender specific cutoff values: 
 
▪ Men: < 383 kcal
 
▪ Women: <270 kcal
 

---------------------------------------	--	---	--

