## 6.6 Physical assessment

### 6.6.1 Weight

Participants weight (in kg) will be recorded at each assessment point on a standard set of calibrated digital scales. Each site will use the same digital scale for all participants.

Additionally, participants will be screened to ascertain if they meet Fried criteria for weight loss (unintentional) of more than 4.5kg in the preceding 12 months.

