## 7 My-AHA Interventions

The intervention in this study is defined as the My-AHA platform. Participants randomized into the intervention arm will have access to the full My-AHA intervention platform (see also Section 8 My-AHA User Platform interface). Participants in the control group will not have access to the intervention package (no treatment control). All participants recruited into the study have no active disease state being treated. All participants meet study criteria for pre-frail status, a non-clinical disease state.

The protocol in the intervention arm is designed to prevent deterioration from a non-clinical state (pre-frail) into the disease state (frail).

The no-intervention control arm will not receive any element of the My-AHA intervention, a no-intervention non-disease control group. Participants in both study arms undergo formal assessment of clinical frailty status at 4 timepoints (baseline, 6 mo, 12 mo, 18mo). **Development of clinical frailty is considered an adverse endpoint for the participant in this study.**

Where a control group participant displays evidence of clinical decline at 6 or 12mo assessment points (defined as meeting clinical criteria for frailty) they will be offered access to the My-AHA intervention suite. We cannot estimate or predict what proportion of the control participants may develop frailty during the 18 month trial as there is no published data on incidence, age-dependent prevalence, or on average rate of decline into frailty from pre-frail states.

Participants randomly allocated to the intervention group will be provided with access to tailored intervention packages. Intervention packages will target domains of pre-frailty (e.g. physical, social, cognitive, nutrition) identified at baseline assessment for each participant. The intervention packages will be revised following each assessment point to accommodate for changes in domain specific areas of pre-frailty.

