## 7.4 Nutritional Interventions

Nutritional interventions will be implemented using a nutrition application (**VitalinQ** - <https://www.vitalinq.nl/>) for mobile devices. The interventions to be deployed include: individual meal plan generation, and tailored nutritional advice and education.

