**PHYSICAL FRAILTY ASSESSMENT**

1	Self-reported weight loss (not due to dieting or fasting) in preceding 12 mo $\geq 4.5$ kg	YES / NO																											
2	Grip strength measured using dynamometer	
  
 Sex	BMI	Grip strength cutoff (kg)	
   
 Male	<math>\leq 24</math>	<math>\leq 29</math>	
 
 	24.1 - 26	<math>\leq 30</math>	
 
 	26.1 - 28	<math>\leq 30</math>	
 
 	<math>> 28</math>	<math>\leq 32</math>	
 
 Female	<math>\leq 23</math>	<math>\leq 17</math>	
 
 	23.1 - 26	<math>\leq 17.3</math>	
 
 	26.1 - 29	<math>\leq 18</math>	
 
 	<math>> 29</math>	<math>\leq 21</math>	
  
 
Is grip strength below cutoff for sex/age?
	Sex	BMI	Grip strength cutoff (kg)	Male	$\leq 24$	$\leq 29$		24.1 - 26	$\leq 30$		26.1 - 28	$\leq 30$		$> 28$	$\leq 32$	Female	$\leq 23$	$\leq 17$		23.1 - 26	$\leq 17.3$		26.1 - 29	$\leq 18$		$> 29$	$\leq 21$
Sex	BMI	Grip strength cutoff (kg)																											
Male	$\leq 24$	$\leq 29$																											
	24.1 - 26	$\leq 30$																											
	26.1 - 28	$\leq 30$																											
	$> 28$	$\leq 32$																											
Female	$\leq 23$	$\leq 17$																											
	23.1 - 26	$\leq 17.3$																											
	26.1 - 29	$\leq 18$																											
	$> 29$	$\leq 21$																											
3a	Ask participant "How often over the past week have you felt that everything you did was an effort?"	YES / NO																											
3b	Ask participant "How often over the past week have you felt that you could not get "going"?"	Score 2 or 3																											

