**B How much weight have you lost in the past 3 months?****[ENTER ONE NUMBER]**

*Please enter the most appropriate number (0, 1, 2 or 3) in the box to the right.*

0 = weight loss greater than 3 kg  
1 = do not know the amount of weight lost  
2 = weight loss between 1 and 3 kg  
3 = no weight loss or weight loss less than 1 kg

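### The follow-up weight-loss criterion (K ≥ 0.05) drops the unintentional condition that its own row heading and the screening rule impose, and no follow-up form shown asks about intent

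*Protocol*

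**What the plan says.** **The criterion.** Protocol section 3.1, Table 2, criterion 1 is shrinking, and the row heading limits it to weight loss that was not intended. The row has two limbs.

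- Screening: "Self-reported weight loss (not due to dieting or fasting) in preceding 12 mo" of at least 4.5 kg. This wording is in Table 2 and again in Appendix 4 (Physical Frailty Assessment, item 1).
- Follow-up: K is the previous-year weight minus the current measured weight, divided by the previous-year weight. A K of 0.05 or more "meets weight loss frailty criteria". No condition on intent follows.

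Section 6.6.1 has weight recorded at each assessment point and adds that participants will be "screened to ascertain if they meet Fried criteria for weight loss (unintentional) of more than 4.5kg in the preceding 12 months". The 5% rule is not mentioned there.

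**How criteria are counted.** Table 2 states "Pre-frail = 1 or 2 of the following criteria are met", and Appendix 4 excludes anyone with none or with more than two. Frail therefore means three or more by implication.

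**What depends on it.** Section 7 names the development of clinical frailty as an adverse endpoint, assessed in both arms. A control participant with decline at 6 or 12 months, "defined as meeting clinical criteria for frailty", is offered access to the intervention.

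**What differs between arms.** Section 7.4 provides "individual meal plan generation, and tailored nutritional advice and education" and section 7.1 provides exercise, both in the intervention arm. Controls receive neither unless they become frail.

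**The concern.** The two limbs of one criterion measure different things. At entry, someone who lost weight by dieting does not score. At follow-up, the same person with the same loss does. An assessor who follows Table 2 literally at 6, 12 or 18 months computes K and marks the criterion as met.

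The outcome is a count with a sharp boundary, and everyone enters at one or two criteria, so one wrongly scored criterion can matter. A participant with two other criteria would be recorded as having reached the adverse endpoint. In a control at month 6 or 12 it could also open access to the intervention, which changes the comparison for the remaining follow-up.

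The exposure that might lead to deliberate loss is not the same in the two arms, so the misclassification need not cancel.

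**Working it through.** The protocol gives no frailty rate or weight-loss rate, so there is no figure of its own to reproduce. The point rests on the text. The arithmetic only shows scale.

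**1. Is intent recorded anywhere after screening?**

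| Source | When used | Asks about intent? |
|---|---|---|
| Appendix 4, item 1 | Screening only (Table 6) | Yes |
| Table 2, follow-up limb (K) | 6, 12, 18 months | No |
| Appendix 6, brief demographic questionnaire | 6, 12, 18 months | No; takes current weight |
| Appendix 23, Self-MNA item B, "How much weight have you lost in the past 3 months" | Follow-up visits | No; amount only, over 3 months |

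The row heading tells the assessor what the criterion is meant to capture, but none of the follow-up forms shown collects the information needed to apply it.

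**2. How do the two thresholds compare?** Loss needed at follow-up = 0.05 × reference weight.

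- 60 kg: 0.05 × 60 = 3.0 kg
- 70 kg: 0.05 × 70 = 3.5 kg
- 80 kg: 0.05 × 80 = 4.0 kg
- 90 kg: 0.05 × 90 = 4.5 kg

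The rules coincide at 4.5 / 0.05 = 90 kg. Below that weight the follow-up rule asks for less loss and also drops the intent condition. Above it, the follow-up rule asks for more loss.

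**3. What could it do to the comparison? (Illustration; every rate is assumed.)** Let p be the true frailty rate in an arm, s the share of its non-frail participants with exactly two other criteria, and q the probability of a deliberate loss of 5% or more, taken as independent of those criteria. Then

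observed rate = p + (1 − p) × s × q.

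Take p = 0.30 in controls and 0.15 in the intervention arm (true difference 15 points), q = 0.20 where deliberate loss occurs, and s = 0.3 or 0.5.

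Intervention arm, if affected:
- s = 0.3: 0.15 + 0.85 × 0.3 × 0.2 = 0.201
- s = 0.5: 0.15 + 0.85 × 0.5 × 0.2 = 0.235

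Control arm, if affected:
- s = 0.3: 0.30 + 0.70 × 0.3 × 0.2 = 0.342
- s = 0.5: 0.30 + 0.70 × 0.5 × 0.2 = 0.370

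| Deliberate loss occurs in | Difference, s = 0.3 | Difference, s = 0.5 |
|---|---|---|
| Intervention arm only | 0.300 − 0.201 = 9.9 points | 0.300 − 0.235 = 6.5 points |
| Both arms equally | 0.342 − 0.201 = 14.1 points | 0.370 − 0.235 = 13.5 points |
| Control arm only | 0.342 − 0.150 = 19.2 points | 0.370 − 0.150 = 22.0 points |

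With 25 per arm, the added intervention events are 25 × 0.051 = 1.3 to 25 × 0.085 = 2.1 people when that arm is affected. The sign of the distortion depends on which arm has more deliberate loss, and the protocol does not say.

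**4. Which weight is the reference?** Table 6 takes weight at screening, baseline, 6, 12 and 18 months. At month 12 the baseline weight, and at month 18 the month-6 weight, is about a year old. At month 6 no study weight is. Baseline would give a window of about 6 months and a recalled weight could give 12. The protocol does not choose.

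**The case against.** The strongest reply is that the row heading governs both limbs, so the formula is merely incomplete under a clear label. That is right about the intended construct. It does not settle practice: the screening limb needed the exclusion spelled out, the follow-up limb lacks it, and intent that was not asked at the visit cannot be recovered in the analysis.

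A reader might go further and infer that the rule adds false frailty events to the intervention arm and so biases against the intervention. The documents do not support that.

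- The nutrition module is not described as a weight-loss programme. Section 7.4.2 speaks of bringing intake to requirements, and section 7.1 lists weight loss among the frailty markers that the interventions target. The programme could equally prevent loss.
- Packages follow each participant's own pre-frailty domains (section 7), so not everyone need receive diet advice.
- Controls who diet are miscounted by the same rule.
- One criterion alone makes nobody frail. Someone losing weight through exercise is also less likely still to meet the low-activity criterion, so the independence assumed in the illustration probably overstates the effect.

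The month-6 reference weight is likewise an ambiguity rather than a failure: a weight from within the previous year does exist. Naming the reference visit might be left to an analysis plan, but Table 2 fixes the formula and the result is used during the trial.

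**Conclusion.** The point holds as an inconsistency within the protocol. The heading and screening limb of criterion 1 require unintentional loss, the follow-up limb does not, and no follow-up form shown could supply the missing condition. Deliberate loss of 5% or more in either arm would count towards the adverse endpoint and towards the control-access trigger.

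Unequal error between arms is possible because diet and exercise components are given in one arm only, but its size and direction are unknown. Under the assumed rates above, a true 15-point difference could appear as anything from 6.5 to 22.0 points. That range shows sensitivity and is not an estimate. The correction is worth making before follow-up visits begin. It does not show that the trial's comparison is biased in a known direction.

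**What to change.** 1. In Table 2, reconcile the follow-up limb with the row heading and the screening limb by attaching the existing dieting-and-fasting exclusion to K ≥ 0.05.
2. Put the existing Appendix 4 question on the follow-up form and ask it identically in both arms at 6, 12 and 18 months.
3. Do not add a separate exemption for loss that participants attribute to the study programme. Only intervention participants, who know their allocation, could use it, so it would remove adverse events from one arm alone.
4. State which recorded weight is the reference at each visit, and say what window this gives at month 6.
5. Reconcile the frailty definition in section 7, including the control-access provision, with the revised Table 2. Which clinical rule should apply there is for the protocol team to decide.

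The cost is one question per follow-up visit and a few lines in Table 2. The small downside is that the follow-up criterion becomes partly self-reported, as it already is at screening. Answers could be coloured by knowledge of allocation, which is why the wording should be the same in both arms.

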**Figure 2: Schematic of Study Design**

**Table 6: Assessment battery for the My-AHA RCT assessment points**

DOMAIN	Test name	Screening	Baseline	6mth	12mth	18mth
Consent process	Information sheets and consent forms (Appendix 1, Appendix 2, Appendix 3)	✓ Appendix x 1	✓			
Screening questionnaire	Screening for inclusion and exclusion criteria; including pre-frail assessment	✓				
Demographic	Standard questionnaire 
 
• Date of birth
 
• Gender
 
• Education (years completed)
 
• Residential status (live alone, with other etc.)
 
• Fear of falls
 
• Falls history
 
• Cognitive activities (mental activity)
 
• Medical history (diseases/diagnoses past and current, medication history)
 
• Continence
 
		✓			
	Brief demographic update questionnaire (to track demographic variables than can change over time): 
 
• Change in residential status since prior assessment
 
• Fear of falls
 
• Falls history since previous assessment
 
• Continence
 
• Cognitive activities (mental activity) since previous assessment
 
• Medical since previous assessment point (diagnoses existing and new, medication prescription current)
 
			✓	✓	✓
RCT Adherence	Cognitive games (in My-AHA platform) time spent in game, time scheduled	✓	✓	✓	✓	
	iStoppFalls – time spent/time scheduled	✓	✓	✓	✓	
	FAME – calendar with diary	✓	✓	✓	✓	
	OTAGO – calendar with diary	✓	✓	✓	✓	
	Endurance training (heart rate monitor, calendar with diary)	✓	✓	✓	✓	
	VitalinQ – time spent/recipes used	✓	✓	✓	✓	
	Technology – duration and frequency of app use	✓	✓	✓	✓	
Health	WHO-QoL OLD	✓	✓	✓	✓	
	Lawton-Brody iADL scale	✓		✓	✓	
Physical	Weight (kg)	✓	✓	✓	✓	✓
	Height (cm)	✓	✓	✓	✓	✓
	Grip strength	✓	✓	✓	✓	✓
	CES-D (2 items assessing exhaustion)	✓	✓	✓	✓	✓
	Time to walk 4m (SPPB)	✓	✓	✓	✓	✓
	IPAQ-Short version	✓	✓	✓	✓	✓

	6-minute walk test	✓	✓	✓	✓
	Short Physical Performance Battery (SPPB)	✓	✓	✓	✓
	Dual-Task Performance (repeat of gait speed test of the SPPB)	✓	✓	✓	✓
	Timed up and Go test	✓	✓	✓	✓
	ABC (self-efficacy for physical function)	✓	✓	✓	✓
	PACES (Physical Activity Enjoyment Scale)				✓
Cognitive	MMSE	✓	✓	✓	✓
	HVLT	✓	✓	✓	✓
	WMS-III Spatial Span (SSP)	✓	✓	✓	✓
	Trail Making Test (TMT-A & TMT-B)	✓	✓	✓	✓
	Stroop test (24 item Victoria Version)	✓	✓	✓	✓
	WAIS-III Digit Symbol substitution (DSS)	✓	✓	✓	✓
Psychological	HADS	✓	✓	✓	✓

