	LSNS-R (Lubben Social Network Scale, Short form)	✓	✓	✓	✓
Social	UCLA Loneliness Scale	✓	✓	✓	✓
	BMI ( derived from height/weight data in Physical battery )	✓	✓	✓	✓
	Self-MNA	✓	✓	✓	✓
Technology	Evaluation of Usability Scale (SUS)				✓
	DART questionnaire				✓
	Computer Literacy Scale (CLS)			✓	
	User Experience Questionnaire (UEQ)				✓
Measures used to determine pre-frailty status of participants (see Table 2)					
Estimated maximum protocol duration:					

 
• Screening assessment – 60 min (1hr)
 
• Baseline assessment – 155 min (2hr 35min)
 
• 6 month assessment – 130 min (2hr 10 min)
 
• 12 month assessment – 135 min (2hr 15 min)
 
• 18 month assessment – 155 min (2hr 35min)
 
					

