**Appendix 9. CES-D 2 item questionnaire**

Participant Code number: \_\_\_\_\_

Study Site: \_\_\_\_\_

Test Phase: Baseline / 6mo / 12mo / 18 mo

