### CES-D

Statement	Rarely or none of the time (less than 1 day)	Some or a little of the time (1-2 days)	Occasionally or a moderate amount of time (3-4 days)	Most or all of the time (5-7 days)
1. How often in the past week have you felt that everything you did was an effort?	1	2	3	4
2. How often in the past week have you felt that you could not get going?	1	2	3	4

Total Score \_\_\_\_\_

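### Table 2 scores the exhaustion answers 2 and 3, but the Appendix 9 form used at baseline and every follow-up prints 3 and 4 under those same answers

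*Protocol*

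**What the plan says.** Protocol section 3.1, Table 2, criterion 3 (poor endurance and energy) treats exhaustion as present on a "response of “2” (a moderate amount of the time, 3-4 days) or “3” (most of the time") to either of two CES-D items. Pairing 2 with 3-4 days and 3 with the top answer implies that the four answers are coded 0, 1, 2, 3.

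Appendix 9 is the form on which the two items are recorded. Its cover reads "Test Phase: Baseline / 6mo / 12mo / 18 mo". Its columns run from less than 1 day to 5-7 days, with the codes 1, 2, 3, 4 printed beneath. Code 2 therefore sits under "Some or a little of the time (1-2 days") and code 3 under "Occasionally or a moderate amount of time (3-4 days"). The form ends with a line for a total.

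Section 6.6.4 lists the four answers in words, without numbers, and refers to Appendix 9. The screening checklist in Appendix 4 asks for a score of 2 or 3, which are Table 2's numbers, but it has no answer key beside them.

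Table 6 schedules "CES-D (2 items assessing exhaustion") across the assessment points and carries the note "Measures used to determine pre-frailty status of participants (see Table 2"). Section 7 states: "Participants in both study arms undergo formal assessment of clinical frailty status at 4 timepoints (baseline, 6 mo, 12 mo, 18mo").

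**The concern.** The numeric rule and the form that supplies the numbers are one code apart, and the protocol gives no conversion. Anyone who applies Table 2's 2 or 3 to the printed Appendix 9 codes picks up 1-2 days, which Table 2's wording does not count. They also miss 5-7 days, which it does.

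The visits affected are the four formal frailty assessments. Section 7 says "Development of clinical frailty is considered an adverse endpoint for the participant in this study". It also provides that a control participant who meets frailty criteria at 6 or 12 months gets access to intervention. A coding slip could therefore change a participant's outcome. In the control arm it could also change what the participant receives, and so the contrast between the arms.

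Table 2 calls a participant pre-frail when 1 or 2 of five criteria are met. Exhaustion is thus decisive for anyone who meets exactly two of the other four.

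**Working it through.** No sample-size or power figure is involved, and the plan states no figure to reproduce. The check sets the two codings side by side and counts answer patterns.

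**Inputs.** The Table 2 rule and its labels (section 3.1); the printed codes (Appendix 9); the pre-frail definition of 1 or 2 of five criteria (Table 2); the screening exclusion at 0 or more than 2 criteria (Appendix 4); 25 participants per arm (section 4).

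**Step 1: the codes.**

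| Answer | Code implied by Table 2 | Code printed in Appendix 9 | Exhausted by Table 2's wording? |
|---|---|---|---|
| less than 1 day | 0 | 1 | no |
| 1-2 days | 1 | 2 | no |
| 3-4 days | 2 | 3 | yes |
| 5-7 days | 3 | 4 | yes |

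The offset is exactly one throughout.

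**Step 2: the answer pairs.** Two items with four answers each give 4 × 4 = 16 pairs. They are written below in the form's printed codes.

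- *Intended rule (Table 2's labels):* either item is 3 or 4. Negative pairs need both items in {1, 2}, which is 2 × 2 = 4. Positive: 16 − 4 = 12.
- *Literal rule on printed codes:* either item is 2 or 3. Negative pairs need both items in {1, 4}, again 4. Positive: 12, but a different 12.
  - False positives: (1,2), (2,1), (2,2), which is 3.
  - False negatives: (1,4), (4,1), (4,4), which is 3.
  - Wrong: 3 + 3 = 6 of 16.
- *Read as 2 or more on printed codes:* only (1,1) is negative. Positive: 15.
  - False positives: the same 3. False negatives: 0.
  - Wrong: 3 of 16.
- *Printed code minus 1, then 2 or 3:* identical to the intended rule. Wrong: 0 of 16.

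The form's total cannot stand in for the item rule. A total of 4 arises from (2,2), negative by Table 2's wording, and from (1,3), positive.

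**Step 3: when the error changes status.** The other four criteria have 2⁴ = 16 met/not-met combinations. Exactly two are met in C(4,2) = 6 of them. In those 6, exhaustion alone decides whether the count is two (pre-frail) or three (beyond pre-frail).

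**Step 4: weight of one error.** With 25 per arm, one misclassified participant moves that arm's frailty proportion by 1/25 = 4 percentage points.

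**The case against.** The strongest reply is that the rule is not really ambiguous. Table 2 gives the answer in words beside each number, section 6.6.4 repeats the words, and the form prints them above its codes. A rater who follows the words classifies correctly. The 6-of-16 reading also requires someone to score 5-7 days as not exhausted while scoring 1-2 days as exhausted, which many would notice. The likelier slip is 2 or more, giving 3 of 16, all in one direction. The form keeps the answer to each item, so subtracting 1 restores the right status, and such recoding could sit in a data dictionary or SAP that is not at hand. The protocol also defines pre-frail but gives no number for frail.

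Much of this stands as to weight. The pattern counts say nothing about how often an error would occur, and the step from more than two criteria to frail is an inference. It does not remove the contradiction. The protocol itself fixes both the numeric rule and the form, and it does not say whether staff score from numbers or labels. The form yields numbers and a total, and the screening checklist states the rule as bare numbers, so numeric scoring is plausible. A later recode repairs the analysis, but it cannot undo a control-access decision already acted on at 6 or 12 months.

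**Conclusion.** The point holds and should be fixed. Table 2 and Appendix 9 assign different numbers to the same answers at all four formal frailty assessments. Applying Table 2's numbers to the form misclassifies 6 of 16 answer pairs on the literal reading, or 3 of 16 if read as 2 or more.

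The conclusion rests on three limits:

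- The counts weight every answer pattern equally. The protocol gives no response distribution, so no rate of misclassified participants can be stated.
- The effect on frailty status takes more than two criteria as beyond pre-frail. That is inferred from the pre-frail definition and agrees with the screening exclusion.
- No error in practice is shown, and none is alleged at screening, where the checklist's numbers match Table 2.

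**What to change.** Reconcile Table 2 and Appendix 9 to one code. Either print 0-3 on the Appendix 9 form, or state the criterion by answer label (3-4 days or 5-7 days on either item) and drop the numbers. Put the same key beside the checklist item in Appendix 4. Say explicitly that the rule is applied to each item separately and not to the form's total.

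Derive frailty status from the answer labels. For any data already recorded on the 1-4 form, subtract 1 before applying 2 or 3. If any control-access determination has already been made from the printed codes, compare it with the labels and document the result.

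The cutoff expressed by Table 2's wording does not change. The cost is a form correction and one derivation line, with no extra visits, staff or participants.
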